## 8 STUDY ASSESSMENTS AND PROCEDURES

- Study procedures are summarized in this section and their timing is presented in the SoA. Protocol waivers or exemptions are not allowed.
- Adherence to the study design requirements, including those specified in the SoA, is essential and required for study conduct.
- All screening evaluations must be completed and reviewed to confirm that potential participants meet all eligibility criteria. The Investigator will maintain a screening log to record details of all participants screened and to confirm eligibility or record reasons for screening failure, as applicable.
- Procedures conducted as part of the participant's routine clinical management (eg, blood count) and obtained before signing of the ICF may be utilized for screening or baseline purposes provided the procedures met the protocol-specified criteria and were performed within the time frame defined in the SoA.
- During the screening period, demography, medical/surgical, and disease history will be evaluated. Demography includes age, gender, race, and ethnicity. Medical/surgical history includes relevant history of previous pathologies and smoking status. Disease history includes stage at diagnosis and at study entry, and previous anti-tumor therapy (type, duration, reason for discontinuation and response to the therapy). In addition, results of driver gene mutation (such as *BRAFV600E* for participants with melanoma) are also to be collected.
- A comprehensive medical history will be assessed for any cardiovascular signs or symptoms prior to treatment, along with a baseline ECG, echocardiogram and troponin level.
- Regular blood samples will be collected from each participant throughout the duration of the study. Repeat or unscheduled samples may be taken for safety reasons or for technical issues with the samples. Details on blood sampling, including the estimated volume collected for each analysis are provided in the laboratory manual.
- For a regional or national emergency declared by a governmental agency, contingency measures are included in [Section 10.11](#).

### 8.1 EFFICACY ASSESSMENTS

The assessment of anti-tumor activity documented by objective response to the IMP is the primary endpoint for this study and is conducted as per schedule provided in the SoA. All participants treated must have at least one measurable lesion for inclusion.

Decision to pursue treatment will be based on the response evaluation made by the Investigator, however, measures of lesions will be collected in the e-CRF for a determination of response by the Sponsor. A partial or complete response must be confirmed on a second examination done at least 4 weeks apart, in order to be documented as a confirmed response to therapy. Confirmation of PD [REDACTED] may be done at the discretion of the Investigator when clinically indicated.

Investigators will obtain copies of the images and will provide them to Sponsor or other repository facility identified by the Sponsor for potential central review. Study sites must retain

tumor assessment images, as Sponsor may decide to collect these images for possible Independent Central Review in the future.

Assessment of tumor response will be conducted using Response Evaluation Criteria in Solid Tumors (RECIST) 1.1 (see [Section 10.9](#) according to the nature of the measurable lesions, as described below).

### **8.1.1 Assessment of objective response using the most appropriate modality according to the nature of the measurable lesion(s)**

For participants with disease that is measured radiologically according to RECIST 1.1 criteria ([Section 10.9](#)) a CT or magnetic resonance imaging (MRI) for tumor assessment will be performed as detailed in [Section 1.3](#). The choice of whether the imaging is by CT (preferred) or MRI is an Investigator decision. Once the choice of CT scan or MRI has been made, the same imaging technique should be used in a participant throughout the trial.

Baseline imaging should include all known target lesions. Baseline scans must evaluate extent of disease, including imaging of head, chest, abdomen (pelvis is optional) and any other locations with suspicion or evidence of disease involvement. This may be accomplished with CT chest, abdomen, and pelvis with contrast, or CT chest with contrast and MRI abdomen/pelvis with gadolinium.

The initial CT/MRI tumor imaging will be performed within 28 days prior to C1D1. Scans performed as part of routine clinical management are acceptable for use as the screening scan if they are of diagnostic quality and performed within 28 days prior to the date of enrollment. On-study imaging will be performed every 9 weeks ( $63 \pm 7$  days) after the date of first IMP and if clinically indicated. Imaging studies should follow calendar days and should not be adjusted for delays in cycle starts or extension. After Week 45 tumor imaging should be performed every 12 weeks ( $84 \pm 7$  days). Per the primary tumor assessment criteria, after the first documentation of response or the first documentation of progression (if the participant is clinically stable), confirmatory imaging may be performed no fewer than 28 days later. Alternately, the scan performed at the next scheduled time point (eg, every  $63 \pm 7$  days) may be used as confirmation. Tumor assessment is not needed for participants who start another anticancer therapy.

At a minimum, all radiologically measurable target lesions (RECIST 1.1) should be imaged at each response assessment. The same radiologic imaging modality should be used at each response assessment.

For participants with no previous history of brain metastases, screening brain imaging will need to be obtained. MRI is the preferred imaging modality however CT is acceptable if an MRI is clinically contraindicated. Two additional imaging, obtained at least 4 weeks apart, should be obtained to document disease stability AFTER local treatment administration to the brain metastases has been completed. If participants receive therapy during these 4 weeks stabilization at the treating physician's discretion, it will be considered as prior anticancer therapy. Participants with previously treated brain metastases may participate provided they are stable, which is defined as lack of progression on two sets of imaging obtained at least 4 weeks apart. Stability as defined above should be documented prior to the first dose of trial treatment. In addition, any neurologic

symptoms must have returned to baseline or resolved, and the participant is not using steroids for at least 14 days prior to study treatment. The screening brain imaging may be collected up to 42 days prior to enrollment.

### **RECIST 1.1** [REDACTED]

RECIST 1.1 will be used as the primary measure for assessment of tumor response, date of disease progression, and as a basis for all protocol guidelines related to disease status (eg, discontinuation of study intervention).

[REDACTED]

## **8.2 SAFETY ASSESSMENTS**

The main anticipated adverse effect for the combination of SAR444245 with other anticancer therapies includes manifestations of cytokine release that can range from fever to hypoxia to hypotension, with or without manifestations that may include any of the organ systems. These mild events occur between around 12 to 18 hours after the first administration and a more intensive monitoring of vital signs is planned during that period. Targeted physical exams and standard laboratory tests will be conducted to monitor potential changes in the main body functions. Measurement of cytokines in plasma are planned at relevant timepoints. White blood cell differential count will be measured to monitor for transient lymphopenia which is commonly observed in the first few days following SAR444245 infusion. Eosinophilia that is surrogate to VLS will also be monitored. IL-5, which is also a marker of VLS, will be included in the PDy cytokine panel. Combining SAR444245 with other anticancer therapies may increase the frequency and severity of immune-related adverse events related to other anticancer therapies. Immune-mediated endocrinopathies involving the thyroid being the most frequent, T3, T4, TSH, and cortisol level will be monitored. When clinically indicated, on-treatment ECG, LVEF and troponin will be assessed and compared to baseline. More details on the safety assessment are provided below. Planned time points for all safety assessments are provided in the SoA.

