### 8.2.2 Vital signs

- Blood pressure and pulse measurements should be preceded by at least 5 minutes of rest for the participant in a quiet setting without distractions (eg, television, cell phones).
- Vital signs including temperature, pulse rate, respiratory rate, and blood pressure will be measured after 5 minutes rest.
- At Cycle 1 Day 1, vital signs after infusion initiation will be collected more intensively;
  - Vital signs will be measured at Pre-dose, 0.5 ( $\pm 0.25$ ), 1 ( $\pm 0.25$ ), 2 ( $\pm 0.5$ ), 4 ( $\pm 0.5$ ) hours after start of SAR444245 dose.
  - At Investigator's discretion, participants (not in the safety run-in) may have intensive vital sign monitoring (to be measured at Pre-dose, 0.5 ( $\pm 0.25$ ), 1 ( $\pm 0.25$ ), 2 ( $\pm 0.5$ ), 4 ( $\pm 0.5$ ), 8 ( $\pm 0.5$ ), 12 ( $\pm 1$ ), 16 ( $\pm 1$ ), 20 ( $\pm 1$ ), 24 ( $\pm 1$ ) hours after start of SAR444245 dose in an in-patient setting).
- **For the core phase participants:** from Cycle 2 to Cycle 4, study therapy will be administered for all patients in out-patient clinic with vital signs taken prior to dosing, at least 4 to 6 hours after the start of SAR444245 dosing, or for longer periods of time if clinically indicated.
- From Cycle 5 and beyond, vital signs will be collected prior to IMP administration.

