- a Blood Chemistry/hematology should be done with an overnight fasting if possible (should not interfere with hydration requirements). It will be performed weekly on D1 pre-dose, D8 and D15 during Cycle 1, then on Day 1 of every cycle up to Cycle 12, then every other cycle during Treatment Phase. During the Observation Period, it will be performed at Follow-Up Visit 1. It can also be performed as clinically indicated. In case of Grade  $\geq 3$  liver function abnormal tests, additional tests will be repeated every 2-3 days until recovery to baseline value.
- b Modification of Diet in Renal Disease (MDRD) equation: Glomerular filtration rate (mL/min/1.73 m^2) =  $175 \times (\text{Serum Creatinine})^{-1.154} \times (\text{Age})^{-0.203} \times (0.742 \text{ if Female}) \times (1.212 \text{ if African American})$
- c Bicarbonate or carbon dioxide (venous) (if bicarbonate or carbon dioxide are assessed only on arterial blood at site level, to be done only if clinically indicated).
- d Urinalysis using dipstick for glucose, blood, pH, protein, ketones, leukocytes and microscopic examination (if blood or protein is abnormal) will be performed every 4 cycles during the Treatment period and as clinically indicated.
- e Pregnancy Test: Women of childbearing potential must have a negative urine pregnancy test result within 72 hours prior to first IMP administration of each cycle, at EOT and every 30 ( $\pm 7$ ) days until 60 days (for Cohort B2) or 120 days (for Cohorts A1, A2 and B1) after the last dose of study treatment. If urine pregnancy results cannot be confirmed as negative, a serum pregnancy test will be required. Pregnancy tests (serum and/or urine tests) should be repeated if required by local guidelines.
- f Participants with known HIV infection under antiretroviral treatment should have HIV viral load & CD4+ count done at screening to confirm controlled infection. Participants with known HBV hepatitis under treatment must have viral load determined at baseline to document controlled infection. Participants with positive serology against HCV must have determination of HCV RNA levels. The need for additional testing due to positive test results will be at the discretion of the Investigator. HIV, hepatitis B and C serology will be tested at screening for participants in Germany and Italy (see [Section 10.8](#)).

Investigators must document their review of each laboratory safety report.

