**Table 8 - Risk assessment**

| Potential risk of clinical significance | Summary of data/rationale for risk   | Mitigation strategy  |
|---|--|--|
| Study intervention(s)            |  |  |
| Infusion-associated reactions           | SAR444245
Not observed in non-clinical toxicology studies.
A minority of patients in the THOR-707-101/HAMMER study have reported such AE as detailed in the IB.                   | SAR444245
Standard pre-medication
Dose modification and treatment guidelines for SAR444245 infusion-associated reactions are provided in individual substudies.   |
| Hypersensitivity, including anaphylaxis | SAR444245
Not observed in non-clinical toxicology studies.
No reports of anaphylaxis in the HAMMER study to date.   | Exclusion of participants with known hypersensitivity to or contraindication any components of SAR444245, PEG, or pegylated drugs.   |
| Infections                              | SAR444245
Nonclinical data do not indicate higher risk for infections.
Adverse events of infections have been reported in the HAMMER study and are presented in the SAR444245 IB. | Routine mitigation:
Participants must have appropriate ANC and other organ/bone marrow function to be included.
During treatment, regular hematology and biochemistry is examined.
Signs and symptoms of infection are monitored as part of TEAE. |

| Potential risk of clinical significance                      | Summary of data/rationale for risk  | Mitigation strategy   |
|--|---|---|
| Cytokine release syndrome                                    | 
SAR444245
 
No major increases in cytokines have been reported in non-clinical toxicology studies.
 
A minority of patients in the HAMMER study have reported such AE as detailed in the IB.
  | 
Study to be conducted at sites experienced with CRS management, with bed available in ICU.
 
Premedication with paracetamol, diphenhydramine (or equivalent medications).
 
Hydration guidelines, including management of anti-hypertensive treatment around the time of infusion, are provided.
 
Extensive post-dosing monitoring will be performed.
 
Dose modification and treatment guidelines are provided in individual substudies.
 |

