### 4.2 SCIENTIFIC RATIONALE FOR STUDY DESIGN

The proposed substudy aims to establish proof-of-concept that non-alpha IL-2 SAR444245 combined with the anti-PD1 antibody pembrolizumab, will result in a significant increase in the percentage of trial participants with HNSCC experiencing an objective response.

This regimen has been already tested and dose confirmed in first in human HAMMER study, therefore this substudy is designed to treat participants only in a core phase.

Please refer to the master protocol for more information.

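### Section 8.2 describes vital-sign and blood-count monitoring at the times toxicity is expected, but outside a safety run-in the required Cycle 1 schedule has no reading or count at those times

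*Protocol*

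**What the plan says.** **Vital signs.** Master protocol Section 8.2 states that mild cytokine-release events "occur between around 12 to 18 hours after the first administration and a more intensive monitoring of vital signs is planned during that period". It sends the reader to the Schedule of Activities for the planned time points. Section 8.2.2 requires Cycle 1 Day 1 readings before dosing and at 0.5, 1, 2 and 4 h; the last is given as "4 ( $\pm 0.5$ ) hours after start of SAR444245 dose". Readings from 8 to 24 h appear only in the next item: "At Investigator's discretion, participants (not in the safety run-in) may have intensive vital sign monitoring", in an in-patient setting. Substudy 01 (Cohort A1) repeats the same rule in its own Section 8.2.2. Because "this substudy is designed to treat participants only in a core phase" (substudy 01, Section 4.2), nobody in Cohort A1 is in a run-in.

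**Blood counts.** Section 8.2 also says: "White blood cell differential count will be measured to monitor for transient lymphopenia which is commonly observed in the first few days" after infusion. For hematology and chemistry, footnote a of Table 7 (Section 10.2) says: "It will be performed weekly on D1 pre-dose, D8 and D15 during Cycle 1". Later counts fall on Day 1 of cycles. The Schedule of Activities agrees, with a ±1 day window on Day 8.

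**Related statements.** The CRS row of Table 8 (Section 10.12) lists as mitigation: "Extensive post-dosing monitoring will be performed". The vascular leak row refers to intensive monitoring on Cycle 1 Day 1 and through the first cycle. CRS of Grade 2 or higher is an adverse event of special interest (Section 8.3.8). The laboratory summary uses each participant's worst on-treatment grade (Section 9.4.3.6).

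**The concern.** A schedule described as planned for a given period and a schedule left to each investigator are different things, and only the second is binding at sites. The consensus grading in Table 11 rests on temperature, blood pressure and oxygen need, and Grade 1 is fever alone. After screening, oxygen saturation is measured only when clinically indicated. If the 12 to 18 h period is observed in some participants and not in others, recorded CRS frequency and grade may partly reflect who was monitored overnight.

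The lymphopenia point is smaller but similar in kind. A worst-grade summary can only use values that were measured. A decrease that is both transient and early can come and go before the first scheduled post-dose count. Anyone who reads Section 8.2 or Table 8 as a description of what is done would expect closer observation than the schedule requires.

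**Working it through.** **1. The plan's own detection figure.** Section 9.2 gives the chance of seeing at least one event in 40 participants as 33.1%, 55.4% and 87.1% for true rates of 1%, 2% and 5%. The formula is 1 − (1 − p)^40.
- p = 0.01: 1 − 0.99^40 = 0.331
- p = 0.02: 1 − 0.98^40 = 0.554
- p = 0.05: 1 − 0.95^40 = 0.871

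The figures reproduce. They assume that every event that occurs is recorded.

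**2. Required vital signs against the 12 to 18 h period** (Section 8.2.2, with windows):

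| Reading | Allowed range (h) | In 12–18 h? |
|---|---|---|
| 0.5 h, required | 0.25–0.75 | no |
| 1 h, required | 0.75–1.25 | no |
| 2 h, required | 1.5–2.5 | no |
| 4 h, required | 3.5–4.5 | no |
| 8 h, optional | 7.5–8.5 | no |
| 12 h, optional | 11–13 | nominal time yes |
| 16 h, optional | 15–17 | yes |
| 20 h, optional | 19–21 | no |
| 24 h, optional | 23–25 | no |

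None of the four required post-dose readings falls in the period. The distance from the last allowed reading to its start is 12 − 4.5 = 7.5 h. The next vital signs in the Schedule of Activities are on Day 8 (±1), which is 144 to 192 h after dosing. The nominal gap is 168 − 4 = 164 h, and the shortest is 144 − 4.5 = 139.5 h.

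**3. Scheduled counts against the first days.** Table 7 footnote a and the Schedule of Activities give Day 1 pre-dose, then Day 8 (±1), which is 6 to 8 days after dosing. No count is scheduled in the first 5 days. The pharmacokinetic flowchart (Section 1.5.1) has a Day 2 sample, but no blood count or vital signs are scheduled with it.

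**4. What incomplete recording could do (illustration only).** The documents give no probability that an event is recorded, so a range s is assumed. For a true 5% event, the chance of recording at least one in 40 is 1 − (1 − 0.05s)^40:
- s = 1: 87.1%
- s = 0.9: 84.1%
- s = 0.75: 78.3%
- s = 0.5: 63.7%
- s = 0.25: 39.5%

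For lymphopenia, Section 4.3 reports Grade 4 decreases at 24 µg/kg in 7 of 11 participants on monotherapy and 3 of 6 with pembrolizumab. If those rates applied to 40 participants, the expected numbers would be 40 × 7/11 = 25.5 and 40 × 3/6 = 20. At s = 0.75 about 19.1 and 15 would be recorded; at s = 0.5, about 12.7 and 10. These show sensitivity to s. They do not estimate this trial's loss.

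**The case against.** The strongest case on the other side is that Section 8.2 is an overview, Section 8.2.2 is explicit, and sites therefore have a clear operative rule. Extended monitoring by choice is a defensible design for a regimen that substudy 01 describes as already tested and dose-confirmed. Section 8.2 itself calls the events mild. Adverse events are collected continuously, the optional series exists, and safety analyses are descriptive. All of this stands, and it limits the consequence. It does not remove the conflict between a period said to have planned monitoring and a schedule that requires none in it.

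On blood counts, it can be said that Section 8.2 describes when lymphopenia occurs, not when counts are taken, and defers timing to the Schedule of Activities. That is partly right: this is a mismatch between a stated purpose and the schedule rather than a flat contradiction.

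Four stronger readings are tempting, and the documents do not support them:
- *Required vital signs stop at 4 h in every cohort.* The wording of Section 8.2.2 implies a separate rule for run-in participants, and the vital-sign sections of the run-in substudies are not in the text at hand.
- *Lymphopenia rates will be biased low against the first-in-human HAMMER study.* HAMMER's safety blood-count schedule is not given; the 72 h and Day 8 samples in Section 4.3 are pharmacodynamic. No nadir time is stated, and no laboratory comparison with HAMMER is planned in the text at hand.
- *CRS is under-detected by a known amount.* Nothing in the documents gives that amount. Grade 2 or higher involves hypotension or an oxygen need, which is likely to come to attention.
- *Table 8 promises monitoring at 12 to 18 h.* It names no hours, and lists other safeguards such as experienced sites and intensive-care access.

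**Conclusion.** The point holds for participants outside a safety run-in, and so for all of Cohort A1. Section 8.2 states that vital-sign monitoring is planned in a period where the binding schedule requires none. It also assigns early lymphopenia to a count that is not scheduled until Day 8 (±1). The vital-sign conflict is the firmer of the two.

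The consequence is possible uneven or incomplete ascertainment of CRS, an event of special interest, and a worst-grade laboratory summary that may miss transient early lymphopenia. The size cannot be derived: it depends on how often the optional series is used, on how many events produce symptoms, and on unscheduled tests. The conclusion rests on the current master and substudy 01 text. The biomarker flowchart is not visible, so early research draws may exist, but they would not be the local safety counts of Table 7.

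**What to change.** - Reconcile Section 8.2 with Section 8.2.2 in the master protocol and in substudy 01, and with Table 7 footnote a and the Schedule of Activities, so that the description and the required schedule agree. Which schedule is right is for the sponsor and investigators to decide; none is proposed here.
- Check that the general monitoring statements in the CRS and vascular leak rows of Table 8 agree with the result, and check the corresponding passages in the other substudies.
- If the 8 to 24 h series stays optional, add one e-CRF field recording whether it was done, and tabulate CRS by that field. The table would be descriptive, since investigators may choose the series for participants they judge to be at higher risk.
- If early counts stay unscheduled, state alongside the reported lymphopenia rates that scheduled counts do not cover the first days after dosing.

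The cost is a wording amendment, one data field, one table and one reporting note.

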### **8.2.1 Physical examinations**

- A full physical examination will include, at a minimum, assessments of the cardiovascular, respiratory, gastrointestinal, neurological and skin systems. Height and weight will also be measured and recorded.

- A directed physical examination will include, at a minimum, assessments of the skin, lungs, cardiovascular system, and abdomen (liver and spleen).
- Investigators should pay special attention to clinical signs related to previous serious illnesses. Investigators should also pay attention to clinical signs suggestive of VLS, such as peripheral edema, pericardial effusion and pleural effusion, as well as clinical signs suggestive of immune-related adverse events, such as pneumonitis, colitis, endocrinopathies, to name a few. Complementary assessments should be performed to establish the diagnosis when clinically indicated. Early signs of CRS should also prompt a thorough clinical assessment to identify the involvement of a specific organ system, including neurological system.

